8. STUDY PROCEDURES

8.1. Screening Period

The screening period is the time from the signing of the informed consent form until start of study treatment or screen failure. Subjects must sign the informed consent form before undergoing screening procedures for this study. Data from laboratory tests and imaging evaluation performed prior to informed consent for routine clinical practice may be used if they are within the specified window period.

Unless otherwise stated, the screening should be completed within 28 days before starting the investigational drug.

- Obtain informed consent form signed by the subject.
- Demographics: gender, date of birth, ethnicity, height, weight, etc.
- Medical history collection:
 - Diagnosis: date of pathological diagnosis, pathological type, clinical stage, B symptoms, and IPS score
 - Treatment history:

- History of radiotherapy: site, dose, and start and completion dates
- History of chemotherapy: regimen, cycles, and start and completion dates
- History of concomitant disease, prior medications, and drug allergies
- Safety assessment (within 14 days prior to the first study dose):
 - ECOG PS;
 - Physical examination: including height, weight, symptoms, and signs. Lymph node regions (for example, submandibular, cervical, supraclavicular, armpit, and groin) and abdominal organs (for example, liver and spleen);
 - Vital signs: body temperature, blood pressure, heart rate, and respiratory rate;
 - Hematology: RBC count, hemoglobin, platelet count, WBC count, neutrophil count, and lymphocyte count;
 - Urinalysis: WBCs, RBCs, and urine protein; if urine protein $\geq 2+$, 24-h urine protein quantitation is required;
 - Fecal occult blood;
 - Hepatic and Renal Function: including ALT, AST, TBIL, ALP, BUN or serum urea level, creatinine, and albumin;
 - Blood electrolytes: including K^+ , Na^+ , Ca^{++} , Mg^{++} , and Cl^- ;
 - Coagulation function: When international normalized ratio (INR) is not available, prothrombin time (PT) will be used;
 - Thyroid function: including TSH, FT3, and FT;
 - Fasting blood glucose;
 - Erythrocyte sedimentation rate;
 - LDH;
 - Virological examination: including HIV-Ab, HBV, and HCV infection testing. HBV testing requirements: HbsAg (qualitative), HbsAb (qualitative), HbcAb (qualitative), HbeAg (qualitative), and HbeAb (qualitative) should be tested at screening. If HBV infection is suspected, HBV-DNA should be tested (qualitatively; if positive, then quantitatively). HCV testing requirements: HCV-Ab is tested at screening to determine the presence of HCV infection. If positive, HCV-RNA will be tested (qualitatively; if positive, then quantitatively).

- Blood HCG test: Only for women of childbearing potential (WOCBP); test within 7 days before the first dose;
- 12-lead ECG;
- Echocardiography;
- Concomitant medication/treatment: Concomitant medications within 14 days before the first dose will be recorded;
- AEs: Document from the signing of informed consent form.
- Efficacy Evaluation
 - Tumor CT or MRI examination: chest, abdomen, pelvis, and other sites of known lesions (perform within 28 days before starting treatment; results of imaging examination performed prior to signing informed consent may be used for tumor assessment at screening if the requirements are met).
 - Tumor FDG-PET examination: Perform within 28 days before starting treatment; results of imaging examination performed prior to signing informed consent may be used for tumor assessment at screening if the requirements are met.
 - Bone marrow aspiration and biopsy. Perform within 28 days before starting treatment; results of bone marrow aspiration and biopsy performed prior to signing informed consent may be used for tumor assessment at screening if the requirements are met.

8.2. Treatment Period

All examinations and evaluations during the treatment period should be completed prior to the administration.

- ECOG PS: Perform within 72 h prior to each dose
- Physical examination: including height, weight, symptoms, and signs. Lymph node regions (for example, submandibular, cervical, supraclavicular, armpit, and groin) and abdominal organs (for example, liver and spleen) are checked within 72 h before each administration;
- Vital signs: including body temperature, blood pressure, heart rate, and respiratory rate; measure within 72 h before each administration;

- Blood HCG test: Only for women of childbearing potential (WOCBP); test within 7 days before the first dose, and at least once every 4 weeks (\pm 7 days) thereafter, regardless of the dosing cycle;
- B symptom assessment: including pyrexia of > 38 °C of unknown cause, night sweats, or weight loss of $> 10\%$ (the evaluation will be conducted on D1 of Cycle 1, and every 2 cycles thereafter until the discontinuation of study treatment);
- PK blood collection: In Cycle 1, within 0.5 h pre-administration and within 5 min and at 2 h (\pm 10 min) post-administration on D1, and on D8 (\pm 60 min). In Cycles 2, 4, and 6, within 0.5 h pre-administration and within 5 min post-administration on D1 (only for subjects participating in the PK study);
- Injection of SHR-1210:
- Adverse event
- Concomitant medication/treatment

The following relevant examinations must be completed pre-administration in Cycle 2 and subsequent cycles (complete within 72 h pre-administration):

- Hematology: RBC count, hemoglobin, platelet count, WBC count, neutrophil count, and lymphocyte count;
- Urinalysis: WBCs, RBCs, and urine protein; if urine protein $\geq 2+$, 24-h urine protein quantitation is required;
- Fecal occult blood;
- Hepatic and Renal Function: including ALT, AST, TBIL, ALP, BUN or serum urea level, creatinine, and albumin;
- Blood electrolytes: including K^+ , Na^+ , Ca^{++} , Mg^{++} , and Cl^- ;
- Coagulation function: When international normalized ratio (INR) is not available, prothrombin time (PT) will be used; once every 2 cycles;
- Thyroid function: including TSH, FT3, and FT; once every 4 cycles
- Fasting blood glucose;
- LDH;

- Virological examination: Only for patients with hepatitis virus infection. Virological examination will be performed every 2 cycles during the treatment period; for patients with HBV infection, they will be tested for HBV-DNA (quantitative), and for patients with HCV infection, they will be tested for HCV-RNA (quantitative);
- 12-lead ECG;
- Tumor CT or MRI examination: Evaluation will be carried out on D1 (\pm 7 days) of Weeks 9, 17, 25, 37, and 49 after the start of treatment, then every 16 weeks (\pm 14 days) until Week 97, and then every 26 weeks (\pm 21 days) until PD (for subjects who continue to receive study treatment after radiographic progression, evaluation will be carried out until the investigational drug is discontinued), start of new anti-tumor treatment, or death;
- Tumor FDG-PET examination: Perform on D1 (\pm 7 days) of Weeks 17 and 25 after the start of treatment. For subjects who have not obtained two negative FDG-PET results after Week 1 and until Week 49, it is necessary to add a tumor FDG-PET examination on D1 (\pm 7 days) of Week 49. If it is necessary to determine whether a radiographic CR is obtained at other unscheduled FDG-PET evaluation time points after the start of treatment, the FDG-PET evaluation must be performed within 4 weeks after the CT evaluation;
- Bone marrow aspiration and biopsy: Patients with bone marrow involvement at baseline require bone marrow aspiration and biopsy to confirm CR status. Bone marrow aspiration and biopsy specimens are collected within 2 weeks after the CT scan. There is no need to perform bone marrow assessment after the bone marrow aspiration and biopsy result turns negative. The subject can start the study treatment before obtaining the bone marrow biopsy result, but the result must be recorded in the subject's CRF.

8.3. End of Treatment

The following examinations are required if tumor CT or MRI has not been performed within 4 weeks and safety evaluation and B symptom assessment have not been completed within 7 days prior to discontinuing the study treatment:

- ECOG PS:
- B symptom assessment: including pyrexia of $> 38^{\circ}\text{C}$ of unknown cause; night sweats; weight loss of $> 10\%$ (symptoms in the past 6 months are evaluated);

- Physical examination: including height, weight, symptoms, and signs. Lymph node regions (for example, submandibular, cervical, supraclavicular, armpit, and groin) and abdominal organs (for example, liver and spleen);
- Vital signs: body temperature, blood pressure, heart rate, and respiratory rate;
- Hematology: RBC count, hemoglobin, platelet count, WBC count, neutrophil count, and lymphocyte count;
- Urinalysis: WBCs, RBCs, and urine protein; if urine protein $\geq 2+$, 24-h urine protein quantitation is required;
- Fecal occult blood;
- Hepatic and Renal Function: including ALT, AST, TBIL, ALP, BUN or serum urea level, creatinine, and albumin;
- Blood electrolytes: including K^+ , Na^+ , Ca^{++} , Mg^{++} , and Cl^- ;
- Coagulation function: When international normalized ratio (INR) is not available, prothrombin time (PT) will be used;
- Thyroid function: including TSH, FT3, and FT;
- Fasting blood glucose;
- LDH;
- Virological examination: Only for patients with hepatitis virus infection. For patients with HBV infection, they will be tested for HBV-DNA (quantitative), and for patients with HCV infection, they will be tested for HCV-RNA (quantitative);
- 12-lead ECG;
- Blood HCG test: for women of childbearing potential (WOCBP) only;
- Tumor CT or MRI examination.

8.4. Follow-Up Period

Subjects enter the follow-up period after the end of treatment. The first visit should be conducted 30 days (± 7 days) after the last dose or on the day of treatment discontinuation (if the date of treatment discontinuation is more than 42 days after the date of the last dose). The second visit is conducted approximately 90 days (± 7 days) after the last dose. Both visits must be conducted at study sites.

- ECOG PS:
- Physical examination: including height, weight, symptoms, and signs. Lymph node regions (for example, submandibular, cervical, supraclavicular, armpit, and groin) and abdominal organs (for example, liver and spleen);
- Vital signs: including body temperature, blood pressure, heart rate, and respiratory rate; measure within 72 h before each administration;
- Hematology: RBC count, hemoglobin, platelet count, WBC count, neutrophil count, and lymphocyte count;
- Urinalysis: WBCs, RBCs, and urine protein; if urine protein $\geq 2+$, 24-h urine protein quantitation is required;
- Fecal occult blood;
- Hepatic and Renal Function: including ALT, AST, TBIL, ALP, BUN or serum urea level, creatinine, and albumin;
- Blood electrolytes: including K^+ , Na^+ , Ca^{++} , Mg^{++} , and Cl^- ;
- Coagulation function: When international normalized ratio (INR) is not available, prothrombin time (PT) will be used;
- Thyroid function: including TSH, FT3, and FT;
- Fasting blood glucose;
- LDH;
- Virological examination: Only for patients with hepatitis virus infection. For patients with HBV infection, they will be tested for HBV-DNA (quantitative), and for patients with HCV infection, they will be tested for HCV-RNA (quantitative);
- AEs: All AEs should be collected until 90 days after the last dose or the start of new anti-tumor treatment. From 30 days after the last dose, for non-serious AEs, only those related to the investigational drug, including AEs of special interest, will be collected. Each recorded AE should be followed up until recovered to baseline level or Grade 0-1, stabilized, or reasonably explained (such as lost to follow-up and death).
- Concomitant medications: collect until 90 days after the last dose of study treatment. After the last dose, only concomitant medications for treatment-related AEs will be recorded.
- Survival follow-up:

- Subjects who discontinue study treatment due to "PD" will begin survival follow-up, which will be conducted every 3 months (\pm 14 days), either via telephone or in-person visit.
- Subjects who discontinue the study treatment due to reasons other than "PD" will enter the tumor progression follow-up, and continue to receive tumor evaluation in accordance with the efficacy evaluation visit frequency (tumor CT or MRI examination, tumor FDG-PET examination) as stipulated in the protocol, until PD, start of new anti-tumor treatment, or death; after tumor progression, the survival follow-up will be carried out once every 3 months (\pm 14 days), either via telephone or in-person visit.

8.5. Unscheduled Visit

The following items should be documented at unscheduled visits for subjects developing AEs during the study:

- Results of relevant examinations
- AEs
- Concomitant medications

8.6. Criteria for Continuing Treatment Beyond Progression

Some subjects receiving immunotherapy can still benefit clinically after radiographic progression. The study treatment may be continued after PD defined per Lugano 2014 criteria for subjects who meet the criteria below:

- The investigators deem that it is in the best interest of the subject to continue treatment, and subject is not required to start other anti-tumor treatment immediately;
- The subject is able to tolerate continued study treatment
- No significant deterioration in subject's performance status, and no significant worsening of cancer-related symptoms
- Before continuing the study treatment, it must be reviewed and approved by the medical monitor

If it is decided that the subject will continue the study treatment after progression, the subject should continue to be treated, evaluated, and followed up according to the protocol requirements.

Subjects should withdraw from study treatment if further progression is observed at the next assessment. The initial date of investigator-assessed progression should be used for all statistics analyses involving progression, regardless of whether the subject continues the study treatment beyond progression.

If the subject discontinues treatment due to deterioration of the general condition without objective evidence for PD, the progression will be reported as "general deterioration". More objective evidences (such as imaging confirmation) of progression of these subjects should be obtained after treatment discontinuation.

For subjects who withdraw from the study due to intolerable toxicity without radiographic PD observed, the imaging examination should be performed at the same frequency, until PD or start of other anti-tumor treatment. The radiographic evidence of PD of these subjects must be obtained whenever possible.

9. ASSESSMENTS

9.1. Assessment of Efficacy

The Lugano 2014 criteria are used to evaluate the objective response rate (ORR), including the CR and PR cases.

ORR: Defined as the proportion of subjects whose best response reaches CR or PR from the first dose to the occurrence of PD or the start of new anti-tumor treatment, whichever comes first

PFS: Defined as the time from the date of the first dose to the first documented PD or all-cause death, whichever occurs first. If the subject has not had PD or died by the data cut-off date, the cut-off date is the date of the subject's last efficacy evaluation. If the subject has not received tumor evaluation, the cut-off date is the date of the first dose, and PFS lasts for 1 day.

DoR: Defined as the time from the date of the first CR or PR to the date of initial assessment of PD or all-cause death, whichever comes first. If the subject has not had PD or died by the data cut-off date, the censoring date is the date of the subject's last efficacy evaluation. Only applicable to subjects with CR/PR.

TTR: Defined as the time from D1 of administration to the first evaluation of PR or CR, whichever comes first. Only applicable to subjects with CR/PR.

9.2. Assessment of Safety

9.2.1. Safety parameters

Safety parameters for this study include clinical symptoms, vital signs, physical examination, and laboratory tests (hematology, urinalysis, blood biochemistry, thyroid function, coagulation function, etc.).

AEs are evaluated according to NCI CTCAE V4.03, including type, incidence, severity, start and end date, whether it is an SAE, correlation with the investigational drug, and outcome.

AEs that occur during the study, including signs and symptoms at screening, will be recorded in the AE page of the electronic case report form (eCRF).

The latest version of MedDRA is used to medically code the collected AEs, which are finally presented in the form of listing.

9.3. Assessment of Pharmacodynamics

PK assessment is conducted by measuring the concentration of the parent drug in the blood sample, and the PK parameters of SHR-1210 in the human body will be calculated using the non-compartmental model. For multiple-dose pharmacokinetics, drug accumulation will be studied according to the maximum concentration and minimum concentration in multiple cycles. The primary multiple-dose PK parameters will be investigated, mainly including:

- 1) C_{\max} : maximum blood concentration;
- 2) C_{\min} : minimum blood concentration;
- 3) T_{\max} : time to the maximum concentration;
- 4) Elimination half-life ($t_{1/2z}$);
- 5) Area under the concentration-time curve (AUC_{τ});
- 6) Apparent volume of distribution (V_z);
- 7) Systemic clearance (CL_s).

10. ADVERSE EVENT REPORTING

10.1. Adverse Event (AE)

10.1.1. Definition of adverse event

An AE refers to any untoward medical occurrence in a clinical investigation subject administered a pharmaceutical product and which does not necessarily have to have a causal relationship with this treatment. In this study, all AEs occurring from signing the informed consent form to 90 days after the last dose will be collected. From 30 days after the last dose, for non-serious AEs, only those related to the investigational drug will be collected.

AEs can include any unfavorable and unintended symptoms, signs, laboratory abnormalities, or diseases, including the following:

- 1) Worsening of pre-existing (prior to entering clinical study) medical conditions/diseases (including worsening symptoms, signs, or laboratory abnormalities);
- 2) Any new AE: Any new adverse medical conditions (including symptoms, signs, and newly diagnosed diseases);
- 3) Clinically significant laboratory abnormalities.

All AEs should be collected in detail by the investigators, including: the name of the AE and description of all relevant symptoms, onset time, severity, correlation with the investigational drug, duration, measures taken, as well as final results and outcomes.

10.1.2. AE severity grading criteria

Please refer to NCI-CTC AE V4.03 for grading criteria. Refer to the following criteria for AEs not listed in NCI-CTC AE V4.03:

Table 3. AE severity grading criteria

Grade	Clinical Description of Severity
1	Mild; asymptomatic or mild clinical symptoms; clinical or laboratory test abnormality only; intervention not indicated
2	Moderate; minimal, local, or non-invasive interventions required; limiting age-appropriate instrumental activities of daily living (ADL), e.g., cooking, shopping, using the telephone, counting money, etc.
3	Severe or medically significant symptoms but not immediately life-threatening; hospitalization or prolongation of hospitalization indicated; disabling; limiting self-care ADL. Self-care ADL: refer to bathing, dressing and undressing, feeding self, using the toilet, taking medications, and not bedridden
4	Life-threatening consequences; urgent intervention indicated
5	Leading to death

10.1.3. Determination of the relationship between AEs and investigational drug

AEs will be collected from the signing of the informed consent form to 90 days after the last study dose or the start of new anti-tumor treatment, regardless of whether the event is related to the investigational drug or whether any medication is taken against the AE. From 30 days after the end of treatment, for non-serious AEs, only those related to the investigational drug will be collected. Any discomforts complained by the subject or changes in objective laboratory measurements during the treatment period should be faithfully recorded. The severity, duration, measures taken, and outcome of AEs should also be documented. The study physician should comprehensively assess the relationship between the AE and the investigational drug by considering the temporal relationship between the administration of investigational drug and the occurrence of AE, the characteristics of the investigational drug, the toxicological and pharmacological effects of the investigational drug, concomitant medications, underlying

diseases, medical history, family history, as well as dechallenge and rechallenge. The causality assessment will be provided using the following five categories: "related, possibly related, unlikely related, not related, and unassessable". Events that are assessed to be "related", "possibly related", and "unassessable" will be listed as adverse drug reactions. When calculating the incidence of AEs, the total of these three categories will be used as the numerator and the total number of subjects for safety assessments will be used as the denominator.

10.2. Serious Adverse Event (SAE)

10.2.1. Definition of SAE

An SAE refers to a medical occurrence during the study that results in hospitalization, prolonged hospitalization, disability, incapacity, life-threatening or death, or congenital malformation. The following medical events are included:

- Events leading to death;
- Life-threatening events (defined as when the subject is at immediate risk of death at the time of the event);
- Events leading to hospitalization or prolonged hospitalization;
- Events leading to permanent or serious disability/incapacity/impairment of work ability;
- Congenital anomalies or birth defects;
- Other important medical events (defined as events that may jeopardize the subject or require interventions to prevent any of the above).

10.2.2. Hospitalization

AEs leading to hospitalization (even if for less than 24 h) or prolonged hospitalization during the clinical study should be considered as SAEs.

Hospitalization does not include the following:

- Hospitalization at a rehabilitation institution
- Hospitalization at a sanatorium
- General emergency admission
- Day surgery (e.g., outpatient/same-day/ambulatory surgery)
- Social reasons (medical insurance reimbursement, etc.)

Hospitalization or prolonged hospitalization unrelated to the worsening of an AE is not an SAE.
For example:

- Hospitalization due to the pre-existing disease without new AEs or aggravation of the pre-existing disease (e.g., hospitalization to examine laboratory abnormalities that have persisted from before the study until now);
- Hospitalization for management reasons (e.g., annual physical examination);
- Hospitalization during the study as specified in the study protocol (e.g., as required by the protocol);
- Elective hospitalization unrelated to worsening of AEs (e.g., elective surgery);
- Scheduled treatment or surgery that should be documented throughout the entire study protocol and/or in the subjects' individual baseline information;
- Hospitalization merely for use of blood products.

Diagnostic or therapeutic invasive (e.g., surgery) and non-invasive procedures should not be reported as AEs. However, when a condition resulting in such procedures meets the definition of AE, it should be reported as such. For example, acute appendicitis during the AE reporting period should be reported as an AE, and the resulting appendectomy should be recorded as the treatment of the AE.

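### Protocol 10.2.2 makes every AE-caused hospitalization an SAE, then takes emergency admissions out of the meaning of hospitalization with no definition and no condition on cause

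*Protocol*

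**What the plan says.** Protocol 10.2.1 lists the seriousness criteria. One of them is "Events leading to hospitalization or prolonged hospitalization". The others (death, threat to life, disability, congenital anomaly, other important medical events) do not depend on hospitalization.

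Protocol 10.2.2 then sets out what counts as hospitalization, in three steps:

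- The rule: "AEs leading to hospitalization (even if for less than 24 h) or prolonged hospitalization during the clinical study should be considered as SAEs".
- A first list, introduced by "Hospitalization does not include the following". Its items are stays in rehabilitation institutions and sanatoria, "General emergency admission", same-day surgery, and social reasons. The lead-in sets no condition on why the patient was admitted.
- A second list, introduced by "Hospitalization or prolonged hospitalization unrelated to the worsening of an AE is not an SAE". Its items are examples under that condition, and the last is "Hospitalization merely for use of blood products".

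Neither the protocol nor the SAP defines the emergency item.

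**The concern.** An acute adverse event often reaches hospital through the emergency route. Of the items in the first list, the emergency one is where a new AE is the most likely cause of the admission. It is also the item whose wording speaks of an admission without saying that inpatient care is excluded. An investigator following the list would conclude that no hospitalization had taken place. An investigator following the opening rule would file an SAE. The synopsis plans approximately 15 sites, so the same event could be classified in two ways within one trial.

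Three things depend on the classification:

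- **Expedited reporting.** Section 10.2.6 requires a report to the drug regulatory and health authorities within 24 hours for SAEs.
- **Safety summaries.** Protocol 12.5.5 and SAP 5.5.2 both provide an SAE summary.
- **Collection itself.** Under 10.1.1, "From 30 days after the last dose, for non-serious AEs, only those related to the investigational drug will be collected".

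Misclassification by this route can only go one way, towards fewer SAEs.

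**Working it through.** The plan states no figure on this point, so there is none to reproduce. The check is to apply the sentences of 10.2.2, with 10.2.1, to the cases a site will meet.

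| Case | Opening rule and 10.2.1 | Lists in 10.2.2 | Result |
|---|---|---|---|
| AE, seen in the emergency room and sent home, no other criterion | Not hospitalized | Not hospitalized | Consistent: not an SAE |
| AE, admitted as an inpatient by a non-emergency route | SAE | Not excluded | Consistent: SAE |
| AE, emergency inpatient admission, also life-threatening or an important medical event | SAE | Admission excluded, but another criterion is met | SAE in either case |
| AE, emergency inpatient admission, no other criterion | SAE | Admission does not count as hospitalization | **Contradiction** |
| Admission to transfuse for a new or worsened cytopenia | SAE | Second list does not apply, because its lead-in requires no link to a worsening AE | Consistent: SAE |
| Admission to transfuse for an unchanged pre-existing cytopenia | No new or worsened AE | Second list applies | Consistent: not an SAE |

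Only the fourth case is contradictory. The section does not say which sentence prevails.

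If a fourth-case event is labelled non-serious, the consequences are as follows:

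1. **Up to 30 days after the last dose.** The event is still recorded as an AE with severity, causality and outcome (10.1.1). It loses the 24-hour report to the authorities (10.2.6) and its line in the SAE summaries.
2. **From 30 days after the last dose.** If judged unrelated to the drug, it is not collected (10.1.1). Section 8.4 words the same rule so that related events, including AEs of special interest, are kept.
3. **After new anti-tumor treatment starts, within 90 days of the last dose.** Section 10.1.3 ends AE collection when new treatment starts, while 10.2.5 keeps SAE reporting going. An event labelled non-serious here can be missed even if it is drug-related.
4. **Beyond 90 days.** Section 10.2.6 provides for reporting only SAEs suspected to be related. Section 7.1.6.1 says that immune-related AEs may appear months after the last dose.

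On scale, take all 60 planned subjects to be in the Safety Set (an assumption). Each subject whose only serious event is of the fourth kind, and whose site follows the list, then lowers subject-level SAE incidence by 1/60 = 1.7 percentage points. The documents do not give the number of such subjects.

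**The case against.** **The phrase may be harmless in intent.** Its neighbours in the first list are settings outside acute inpatient care, so it can be read as emergency-room attendance without admission. The opening rule, which reaches stays under 24 hours, also weighs against excluding a true admission. This is a fair reading and may be the intended one. However, the text says admission and the documents nowhere state the narrower meaning, so the conflict remains on the page.

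**Other provisions catch many events.** The important-medical-event criterion in 10.2.1 fits many acute admissions. Section 10.4 sends several event types to the sponsor within 24 hours, serious or not: infusion reactions of Grade 3 or higher; diarrhea or colitis, uveitis and interstitial pneumonia of Grade 2 or higher; other immune-related events of Grade 3 or higher; and Hy's Law cases. Monitoring and medical review (13.2, 13.3.3) also check the data. These provisions narrow the gap but do not close it. The 10.2.1 criterion is a matter of judgment. The special-interest report goes to the sponsor, with the authorities added only if the event is also an SAE. A non-immune acute event, such as an infection, has no special-interest route unless it falls under one of the listed types.

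**Stronger readings that the documents do not support:**

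- A reader might infer that the blood-product item also exempts transfusion admissions for treatment-emergent cytopenia. It does not, because its lead-in limits it to admissions unrelated to the worsening of an AE. It can be misapplied, since it does not repeat the condition as some neighbouring items do, but it does not contradict the rule.
- A reader might put a figure on the loss. For example, assume that 15% to 30% of 60 subjects have a hospitalization SAE, and that 20% to 50% of those enter only by emergency admission and meet no other criterion. The result is 60 × 0.15 × 0.20 = 1.8 to 60 × 0.30 × 0.50 = 9 subjects, or 3% to 15%. Neither pair of rates is in the documents, and the calculation also assumes that every site applies the literal reading. If none does, the loss is 0.
- A reader might blame the lack of a described data monitoring committee. Investigators complete the SAE form, and the documents give no committee the task of checking seriousness.

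**Conclusion.** Section 10.2.2 contradicts itself on one item. An AE whose sole seriousness criterion is an emergency inpatient admission is an SAE under the opening rule and not under the first list. Applied literally, the list removes the event from expedited reporting and the SAE summaries and, in the late windows described above, can remove it from the data.

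The size cannot be estimated from the documents. It runs from zero, if sites take the phrase as emergency-room attendance, up to an unknown number of events at 1.7 percentage points per affected subject. The contradiction rests on the text alone. Any numerical loss would need three further things: sites applying the list as written, events with no other seriousness criterion, and affected subjects with no other SAE.

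The point concerns safety reporting only. ORR, sample size and error rates are unaffected. It is worth correcting because the misclassification can only lower the SAE count and the remedy is a small wording change.

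**What to change.** In protocol 10.2.2:

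- Replace the emergency item with: *emergency-department attendance that does not lead to inpatient admission*.
- Add one sentence: *an inpatient admission caused by a new or worsened AE is an SAE whatever the route of entry*.
- Optionally, repeat in the blood-product item the condition from its lead-in, that the admission is unrelated to the worsening of an AE.

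The cost is a few phrases in the protocol and a note to sites, with a slightly higher SAE count and a few more SAE forms. The efficacy analysis does not change.
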